2. POTENTIAL BENEFITS OF THE PROPOSED RESEARCH TO THE SUBJECT AND OTHERS

All participants will receive a 3-session behavioral intervention with demonstrated efficacy in the treatment of Cannabis Use Disorder (Brief Marijuana Dependence Counseling). This treatment will be provided at no charge. Participants will also have the ability to receive study-rTMS, which may reduce their craving for cannabis or help them reduce their cannabis use. In addition to the potential direct benefits of participation in this study, participants will also help investigators understand the utility of rTMS as a potential treatment for Cannabis Use Disorder.

3. IMPORTANCE OF THE KNOWLEDGE TO BE GAINED

This study may provide important information that can improve treatment for future patients with Cannabis and other substance use disorders.

4. RISK BENEFIT ASSESSMENT FOR THE PROPOSED RESEARCH

All of the procedures we will perform as part of this trial are low-risk, and each said risk has been minimized. Each participant will receive a standard of care behavioral treatment for Cannabis Use Disorder, and a promising candidate-treatment. We subsequently believe that the risk-benefit ratio is favorable for each individual participant. We also believe the data obtained in this trial has the potential to benefit society by developing this candidate-treatment.

5. DATA AND SAFETY MONITORING PLAN This section is based on the recommendations in NIDA's "Guidelines for Developing a Data and Safety Monitoring Plan" (www.drugabuse.gov/funding/dsmbsopt.html). A detailed DSMP will be developed and approved by NIH program staff prior to study initiation.

a. Summary of the Protocol.

This application proposes to investigate the effects of rTMS on craving and cannabis use in Cannabis Use Disordered participants. The primary outcomes of interest are cannabis cue induced craving (Aim 1), and cue reactivity in reward network areas (Aim 2). Inclusion/exclusion criteria are outlined above. Power calculations and sample sizes are in the Data Analysis Plan section above.

b. Trial Management.

The study will be managed from the Brain Stimulation Lab within the Department of Psychiatry and Behavioral Sciences at Stanford University. The target population is described above in the inclusion/exclusion criteria.

c. Data Management and Analysis.

Data will be entered by research team-members directly into REDCap, and fMRI data will be kept on secure Stanford servers.

d. Quality Assurance.

We will conduct quarterly data audits. Confidentiality protections are outlined above.

e. Regulatory Issues.

Potential conflicts of interest will be reported using the NIH rules for disclosure. Adverse Events (AEs)/Serious Adverse Events (SAEs) occurring during the course of the project will be collected, documented,

and reported in accordance with protocol and IRB reporting requirements. All research staff involved with adverse event reporting will receive general and protocol specific AE/SAE training including identification, assessment and evaluation, and documentation and reporting. A research specialist will identify any potential adverse events during the course of the study from participant self-report and administration of the visit assessments and procedures. The research specialist will provide information to a study physician, who will be responsible for AE/SAE assessment and evaluation including a determination of seriousness and study relatedness.

f. Definition of AE and SAE.

An Adverse Event (AE) is defined as any untoward medical occurrence in a study subject administered a medical treatment that does not necessarily have a causal relationship with this treatment (ICH GCP). Any unwanted change, physically, psychologically or behaviorally, that occurs in a study participant during the course of the trial is an adverse event. A Serious Adverse Event (SAE) is defined as an adverse event that has one of the following outcomes:

- Results in death
- Is life-threatening
- Requires inpatient hospitalization or prolongation of existing hospitalization
- Results in persistent or significant disability/incapacity
- Is a congenital anomaly/birth defect OR
- Requires intervention to prevent one of the above outcomes.

g. Documentation and Reporting.

AEs/SAEs are documented and reported as per protocol and IRB requirements. Research staff will identify adverse events and obtain all available information to assess severity, seriousness, study relatedness, expectedness, outcome and the need for change or discontinuation in the study intervention. Review of Adverse Events: Adverse events (AEs) will be assessed at each visit by study personnel. The type of AE, severity of AE, and the relationship to the application of rTMS will be recorded. AEs will be coded using Medical Dictionary for Regulatory Activities (MedDRA) rules. Adverse events are generally documented on AE Logs and AE Case Report Forms (CRFs). Additional relevant AE information if available should be documented in a progress note in the research record as appropriate to allow monitoring and evaluating of the AE. If the AE meets the definition for serious, appropriate SAE protocol specific reporting forms are completed and disseminated to the appropriate persons and within the designated timeframes as indicated above. For each AE/SAE recorded, the research staff will follow the AE/SAE until resolution, stabilization or until the participant is no longer in the study as stated in the protocol. When a reportable SAE is identified, the research team will notify the Stanford Institutional Review Board (IRB) within 24 hours.

Other adverse events will be reported to the Stanford IRB if the AE is unexpected AND related or possibly related AND serious or more prevalent than expected. All three criteria must be met for an AE to be reported to the Stanford IRB. The IRB definition of unexpected is that the AE is not identified in nature, severity or frequency in the current protocol, informed consent, investigator brochure or with other current risk information. The definition of related is that there is a reasonable possibility that the adverse event may have been caused by the intervention. Reportable AEs are reviewed by the IRB Chair and reported to the IRB Board at the next meeting.

h. Trial Safety.

The potential risks and benefits and methods to minimize these risks are outlined above. The research team will report any unexpected AEs or any scores of "severe" on the side-effect symptom rating form or any FDA-defined serious AEs to the PI within 24 hrs so that the PI can decide on the appropriate action. All unexpected AEs will be monitored while they are active to determine if treatment is needed. Study procedures will follow the FDA's Good Clinical Practice Guidelines (www.fda.gov/oc/gcp). Any outside requests for information or any breaches in confidentiality will be reported to [name].

An interim analysis is not planned at this time.

i. DSM Plan Administration.

[name] will be responsible for monitoring the study and will participate in weekly study team meetings.

i. DSM Board.

A Data Safety and Monitoring Board will be formed to monitor both the rate and severity of adverse events. This panel will include an expert in addictions clinical-trials ([name] MD), an expert in brain stimulation ([name] MD MSCR), an expert in neuroimaging ([name] PhD), and a biostatistician with expertise in addictions clinical trials ([name] MS). The DSM Board will meet twice-yearly while the study is recruiting.

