To assess group differences in the number of weeks of abstinence in the follow-up period (Aim-2a), a Poisson regression model was fit with the total number of weeks of self-reported abstinence in the four-week follow-up period as the dependent variable and treatment, site, and treatment by site interaction as independent variables. We conservatively imputed missing values as non-abstinent, thereby including the total ITT sample. We additionally performed a sensitivity analysis for weeks of abstinence by including the weeks preceding the 9th rTMS-treatment visit and immediate post-visit since these two weeks represent the time following the delivery of a total of 16-sessions of rTMS (a similar dose to early rTMS for depression studies). We calculated the relative risk of having a week of abstinence as a measure of the effect size, along with 95% confidence intervals. We used creatinine-corrected urine cannabinoids to verify self-reported abstinence at follow-up weeks 2 and 4, and calculated the proportion that these two methods were concordant.

To evaluate group differences in the number of days of cannabis use (Aim-2b), we utilized a GLMM with the number of days-per-week of cannabis use as the dependent measure. We included participants in the model who had follow-up data (the completer sample; N=51) and given the apparent divergence in days-per-week of cannabis use in the final two-weeks of the follow-up period, we chose to focus our analysis on that period.

Residual normality was assessed for each of the above models using QQ-plots. We included sex in all models to detect a potential effect, but when no significant effects were found, we excluded sex from the subsequent final models. Apart from craving, this was a pilot trial and not powered a priori to detect statistically significant differences; however, statistically significant *p*-values are noted when observed. When reported, a level of $\alpha = 0.05$ was used (two-tailed), and no adjustments for multiple comparisons were made for this preliminary investigation. Effect sizes at each time point were estimated as Cohens d using means and pooled standard deviations. Statistical analyses were conducted using R software (version 4.2.1, GNU project) and SAS version 9.4 (Cary, NC).

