To date there has been limited work examining the effect of rTMS on aspects of CUD. Drawing from the published literature suggesting that excitatory rTMS applied to the DLPFC can reduce craving, the candidate and mentorship team recently completed a preliminary sham-controlled crossover study in cannabis use disordered individuals. The trial suggested that rTMS is safe and well-tolerated, and that a single session of rTMS *acutely* decreases cannabis cue-induced craving. The promising results from our single session trial parallel the single session results found in nicotine and cocaine use disordered populations which subsequently translated into positive multiple session clinical trials(8, 9). As such, it follows that a trial utilizing multiple sessions of rTMS in cannabis use disordered patients may yield positive results.

The overarching goal of this proposal is to investigate if a course of excitatory DLPFC rTMS results in reduced cannabis cue-induced craving in treatment seeking individuals with CUD (Aim1). Additionally, we seek to explore the mechanistic underpinnings of any observed effect by collecting functional magnetic resonance imaging (fMRI) data during cannabis cue-administration before and after the treatment course (Aim 2). These aims will be addressed through a double-blind, randomized, sham-controlled study in which 72 treatment seeking cannabis use disordered participants (36/group) will be given 20 sessions of either *Active* or *Sham* excitatory rTMS applied to the DLPFC. rTMS will be delivered in an accelerated fashion as quickly as in two-weeks, but most often over five-weeks (2 sessions each day, 10 treatment-days). rTMS will be applied in conjunction with a validated three-session Motivational Enhancement Therapy (MET) behavioral intervention.

Aim 1: Determine if a course of excitatory rTMS applied to the DLPFC results in reduced cue-induced craving. We hypothesize that as compared to participants receiving sham rTMS, participants receiving active rTMS will have a reduced level of cannabis cue-induced craving following their final rTMS session as compared to prior to their first rTMS session. We will measure self-reported cannabis craving during a validated cannabis cue-reactivity paradigm, and define cue-induced craving as change in self-reported craving from pre-to-post cue administration.

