General Overview (Figure 3): The primary aims are to determine the efficacy of 20 sessions of DLPFC rTMS in decreasing cannabis cue-induced craving (Aim 1) and cue reactivity in a validated fMRI paradigm (Aim 2). The aims of the study will be accomplished by performing a double-blind, randomized, sham controlled clinical trial with two arms. Individuals with CUD will be

recruited from the community. All participants will receive a three-week behavioral intervention and adjunctively undergo a course of either *active* or *sham* rTMS during that time. Post-treatment

outcomes will be assessed at two- and four- weeks following completion of the rTMS course.

Screening: Participants will meet with study personnel either in person, or via Stanford Secure Zoom, and complete

assessments about substance use, psychiatric and medical history. Eligible participants will complete questionnaires and provide a urine sample for drug screening. For females, a pregnancy test will be done prior to the drug screen. Pregnant women will not be allowed to participate.

rTMS Sessions: rTMS will be delivered via a MagPro double blinded rTMS Research System (MagVenture, Denmark) with a Cool-B65 Butterfly Coil (a combined active and sham coil). We will use a standard resting motor threshold (rMT) determination to determine the TMS dose (42). Treatment will be delivered at 120% rMT. Each active rTMS study-treatment will consist of a total of 4000 pulses of 10Hz stimulation (5s-on,10s-off). Treatments will be delivered at the EEG coordinate for F3 (which approximates the left DLPFC), and will be found using the Beam-F3 method (43). This is a treatment paradigm that has been used extensively in other trials (25, 44-46). Sham sessions will be delivered using an electronic sham system consisting of a coil that mimics the appearance and sound of rTMS, combined with a TENS device which produces a small electric shock mimicking the feeling of active rTMS. This type of sham has been demonstrated to be indistinguishable from active rTMS, has been well tolerated in (21, 25), and successfully used in other clinical trials(47, 48).

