Statistical Analysis: Baseline demographic and clinical measures will be compared across treatment groups using standard statistical methods (i.e., categorical variables compared using Pearson chi square test of independence; continuous variables compared using univariate ANOVAs). Characteristics that display imbalance at the baseline measure, association with the dependent variable, or are known to be predictive of cue induced craving, reactivity, or cannabis-use outcomes will be assessed for inclusion as covariates in the final models. To test our primary hypothesis that a full course of active excitatory rTMS will reduce cue induced craving as compared to sham rTMS (Aim 1), generalized linear mixed effects models will be constructed to estimate treatment group differences in craving scores. Overall statistical significance for the effects of treatment group, time, and their interaction will be assessed using a likelihood ratio test that compares the final model, to a model consisting of an intercept term alone. The hypothesis that those receiving active rTMS will have decreased craving will be tested using model-based estimates to construct group level comparisons across all the planned time points. Normality of residuals will be tested for these models and when found in error, appropriate transformations or non-parametric methods will be conducted. For Aim 2 (evaluating the impact of rTMS on cannabis CR), BOLD response during the cannabis cue vs. neutral cue trials will be the primary contrast of interest to test hypotheses. Where significant differences are observed, parameter estimates from task-based models, from each ROI will be extracted and relations with clinical endpoints examined. For our exploratory Aim: The primary analysis will involve preliminarily investigating the efficacy of active rTMS, compared to sham rTMS in increasing the proportion of cannabis abstinent participants during the final two weeks of study treatment (four-week follow-up). A combination of self-reported abstinence from

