Sample Size Justification: The primary focus of this study is to show evidence, with sufficient strength, that treatment with active rTMS will result in decreased cue induced craving (Aim 1), and decreased BOLD response in reward network structures during a cue-reactivity fMRI paradigm (Aim 2) in CUD participants treated with either active or sham rTMS. For Aim 1: Within subject craving measures tend to be highly correlated when measured closely in time and thus we assume a conservative ICC of $p=0.75$ (previous CUD studies range $p=0.60-0.75$) with a standard deviation of ≈ 12.2 . We intend to detect a clinically meaningful craving score difference between the two treatment groups of 8.5 (Cohen's $d=8.5/12.2\approx 0.7$). This is a conservative estimate given that recent multi-session rTMS treatment trials have yielded larger effect sizes on craving ($d=0.98$ (7) in alcohol users, and $d=0.84$ (9) in cocaine users). In the proposed study we will measure increased craving (via MCQ total score) following the presentation of a validated cannabis cue paradigm both before and after a treatment course of rTMS. Under the assumption of independent observations, a total sample size of 32 participants equally allocated to each treatment assignments will provide 80% power with a type 1 error rate of 5% to detect the stated effect size of 0.7. However, the effective sample size in a repeated measures data setting is reduced when assuming an ICC of 0.75. The number of participants per group required is therefore estimated to be $n=27$. Additionally, we need to adjust for study attrition between randomization and the 4-week follow up visit. Assuming an attrition rate of up to 25%, a sample size of **36 participants randomized to each treatment group (n=72 total)** will provide adequate power to detect the primary aim effect size of $d=0.7$ between those receiving active and sham rTMS. **For Aim 2:** In a within subjects investigation of nicotine use disordered participants undergoing a single session of rTMS, there was a significant effect on BOLD response to smoking cues (see figure 2, Preliminary Studies section). If we assume that, as with previous study of cue induced BOLD reactivity in smokers using rTMS, our effects are of medium to large size (e.g. $d=0.7-0.8$) with alpha =5% (2-tailed), a sample of **36 randomized participants in each group will result in greater than 80% power for detecting effects of treatment on CR-BOLD response**. In sum, we are confident that the proposed randomized sample size of 72 participants will be sufficient to test Aims 1 and 2. **For our exploratory Aim**, our recent, non-contingency management based medication trials for cannabis cessation have shown varying placebo abstinence rates (defined as ≤ 50 ng/ml THCCOOH UCT) at the end of study (EOS) treatment (5-15%) (38, 39, 41). Since we are only hoping to provide preliminary data to power a more definitive study, our sample is not designed to sufficiently answer this question definitively. Despite this fact we will still have power to detect a large effect on abstinence. An rTMS abstinence rate of at least 30% greater than placebo at the end of study treatment under the most conservative conditions, at a 10% placebo abstinence rate, a randomized sample size of 36 participants in each treatment group will provide 80% power with a type 1 error of 5% to detect this difference at the end of this pilot study.

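### Craving and BOLD cue reactivity are both called primary, each sized at 5%, with no testing order or success rule, although other text favours craving

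*Combined protocol and SAP*

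**What the plan says.** Three places in the combined protocol and SAP put the two outcomes side by side at trial level.

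- Section D, General Overview: "The primary aims are to determine the efficacy of 20 sessions of DLPFC rTMS in decreasing cannabis cue-induced craving (Aim 1) and cue reactivity" (the sentence goes on to name the fMRI paradigm as Aim 2).
- Sample Size Justification: the opening sentence makes both aims the study's primary focus. The summary after the Aim 2 paragraph reads "In sum, we are confident that the proposed randomized sample size of 72 participants will be sufficient to test Aims 1 and 2".
- Section E.5.a, Summary of the Protocol: "The primary outcomes of interest are cannabis cue induced craving (Aim 1), and cue reactivity in reward network areas (Aim 2".

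Each aim has its own error rate. For Aim 1 the stated number "will provide 80% power with a type 1 error rate of 5% to detect the stated effect size of 0.7". Aim 2 is sized "with alpha =5% (2-tailed") at d = 0.7-0.8, with power above 80% claimed for 36 per group.

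Other text favours craving.

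- Statistical Analysis: "To test our primary hypothesis that a full course of active excitatory rTMS will reduce cue induced craving as compared to sham rTMS (Aim 1").
- Specific Aims: craving comes first, and then "we seek to explore the mechanistic underpinnings of any observed effect by collecting functional magnetic resonance imaging (fMRI) data".
- Sample Size Justification: the 36 per group is derived from Aim 1, whose d = 0.7 is described as the effect size of the primary aim, in the singular.
- 2023 SAP: craving is the one exception to its statement that this pilot was not powered in advance. It adds that "no adjustments for multiple comparisons were made for this preliminary investigation".

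The 2023 SAP has no BOLD analysis. Its Aim-2a and Aim-2b are weeks of abstinence and days of cannabis use.

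**The concern.** With two outcomes called primary and no rule joining them, a null craving result with a significant BOLD result, or the reverse, could be presented as a positive primary finding at p < 0.05. The documents do not say whether such a trial succeeded. If either result is enough, the 5% error rate attached to each aim does not hold for the pair. If both are needed, the single-aim power figures do not describe the chance of success. A reader comparing the protocol with the SAP also cannot tell whether BOLD was ever meant to decide the trial, because the SAP gives the Aim 2 label to other outcomes.

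**Working it through.** **Inputs from the Sample Size Justification.** Alpha 5% (two-sided for Aim 2; the SAP is two-tailed throughout); Aim 1 d = 8.5/12.2 ≈ 0.7; ICC 0.75; 27 per group after the ICC; attrition up to 25%; 36 per group randomised; Aim 2 d = 0.7-0.8.

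**Not in the documents, so assumed.** The correlation ρ between the two test statistics, shown over 0 to 0.8. The number of repeated craving measures behind the 27 is also not stated; three is inferred below. One test per outcome is assumed.

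**Step 1: reproduce the plan's figures (normal approximation).**

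- Independent observations: 2 × (1.96 + 0.84)² / 0.7² = 32.0. The stated 32 therefore reproduces as a number per group.
- ICC factor (1 + (m − 1) × 0.75)/m applied to 32.04: m = 2 gives 28.0, m = 3 gives 26.7, m = 4 gives 26.0. Three measures (factor 2.5/3 = 0.833) round up to the stated 27.
- Attrition: 27/0.75 = 36.
- Aim 2 at 36 per group: Φ(0.7 × √18 − 1.96) = 84.4% and Φ(0.8 × √18 − 1.96) = 92.4%. The claim of more than 80% reproduces.

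**Step 2: either outcome is enough, both nulls true.** Two-sided error = 1 − P(|Z₁| < 1.96 and |Z₂| < 1.96). At ρ = 0 this is 1 − 0.95² = 9.75%. The error of claiming benefit for active rTMS is 1 − P(Z₁ < 1.96 and Z₂ < 1.96); at ρ = 0, 1 − 0.975² = 4.9%.

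| ρ | Two-sided, either | False claim of benefit |
|---|---|---|
| 0 | 9.75% | 4.9% |
| 0.3 | 9.5% | 4.8% |
| 0.5 | 9.1% | 4.5% |
| 0.7 | 8.3% | 4.2% |
| 0.8 | 7.8% | 3.9% |

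The single-test values are 5% and 2.5%.

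**Step 3: both outcomes required.** Aim 1 power, with the plan's repeated-measures gain, is Φ(0.7 × √(n/2)/√0.833 − 1.96): 80.4% at n = 27 and 90.2% at n = 36. Aim 2 power is Φ(d × √(n/2) − 1.96): 73.0% and 83.6% at n = 27, and 84.4% and 92.4% at n = 36, for d = 0.7 and 0.8. Joint power is the bivariate normal probability that both tests are significant; at ρ = 0 it is the product, for example 0.804 × 0.730 = 58.7%.

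| Per arm, both outcomes | BOLD d | ρ = 0 | ρ = 0.3 | ρ = 0.5 | ρ = 0.8 |
|---|---|---|---|---|---|
| 27 (25% attrition) | 0.7 | 58.7% | 61.7% | 64.0% | 68.4% |
| 27 (25% attrition) | 0.8 | 67.3% | 69.6% | 71.5% | 75.3% |
| 36 (no loss) | 0.7 | 76.1% | 77.6% | 78.9% | 81.6% |
| 36 (no loss) | 0.8 | 83.4% | 84.3% | 85.2% | 87.3% |

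Using t-test power for Aim 2 (71.4% at 27 and 83.4% at 36, d = 0.7) lowers the smallest entries to 0.804 × 0.714 = 57.4% and 0.902 × 0.834 = 75.2%. The ranges are therefore about 57-75% at 27 per arm and about 75-87% at 36 per arm. In the table, 11 of the 16 cells lie below 80%. The five that do not all need zero attrition, plus either d = 0.8 for BOLD or ρ = 0.8.

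**The case against.** The strongest reply is that craving already leads. The Statistical Analysis section has one primary hypothesis, craving; the sample size is built on Aim 1; and fMRI is introduced as exploring the mechanism of an effect. That stands against any reading that the two outcomes have equal rank throughout. It does not supply a testing order, and it conflicts with the three places that pair them.

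The assessment schedule also lists a primary outcome under every aim, including the exploratory one, so the word may mean the lead measure within an aim. That explains the schedule. It does not explain the General Overview, the sample-size section or the monitoring plan, which name Aims 1 and 2 for the trial and leave the exploratory aim out.

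Third, this is a preliminary investigation, the SAP discloses that it made no adjustment, and neither document proposes an either or a both claim. This is fair. The SAP statement covers a set of analyses without BOLD, so it cannot be read as a decision to test the craving and BOLD pair unadjusted.

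Three stronger inferences are not supported. A reader might take 9-10% as the false-efficacy rate; it counts results in either direction and needs ρ of about 0.5 or less. A reader might conclude that power for both always falls short of 80%; with no loss it need not. A reader might infer that a primary outcome was dropped; the absence of BOLD from the SAP shows only that the two documents disagree about Aim 2.

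**Conclusion.** The point holds as an unresolved ambiguity about what is primary. The protocol calls both outcomes primary at trial level and sizes each at 5% without a rule for combining them, while other passages and the SAP point to craving. Under an either rule the error rate is roughly 1.6 to 1.95 times that of one test, both two-sided and in the direction of benefit. Under a both rule the shortfall from 80% is clear with the planned attrition and depends on the scenario without it. The zero-loss case looks optimistic: the SAP reports follow-up data for 51 of 72 (29% missing), although that counts follow-up data and not scans.

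These sizes rest on an assumed correlation, an inferred three craving measures and a single test per outcome. The protocol names no single BOLD region, so the either error could be higher. The remedy is cheap and follows the sponsor's own leaning, so it should be made.

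**What to change.** State that cue-induced craving (Aim 1) is the single primary outcome, tested at two-sided 5%. State that BOLD cue reactivity (Aim 2) is a key secondary, mechanistic outcome, tested at two-sided 5% only if Aim 1 is significant, and otherwise reported as an exploratory estimate with a confidence interval.

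Align the wording where it stands:

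- General Overview: the reference to primary aims.
- Sample Size Justification: the reference to the primary focus.
- Schedule of visits and assessments: the primary-outcome label for Aim 2.
- Section E.5.a: the reference to primary outcomes.
- SAP: the Aim-2a and Aim-2b labels, with a statement of where BOLD is analysed.

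Because the SAP reports completed analyses, record this as a dated clarification and do not present it as prespecification.

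Aim 1 loses no alpha or power, and the sequence keeps the family-wise error at 5% or less. By comparison, a 2.5% split would cut Aim 1 power to about 72% at 27 per group (three measures). The cost falls on Aim 2: a BOLD effect without a craving effect can be reported only as exploratory, and the chance of a confirmatory BOLD finding becomes the joint power shown above.
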